H2: Babies born to mothers treated in CC centers will have higher birth weights on average compared to babies born to mothers treated in ECHO centers.

- 3) To determine differences in obstetrical providers' work satisfaction among the two treatment models according to the **Physicians Worklife Survey**.

H3: Obstetrical providers randomized to the CC compared to the ECHO condition will score higher on subscales (autonomy, relationship with patients, patient care issues and relationship with staff) of the Physicians Worklife Survey.

Primary, secondary and exploratory outcomes are listed in the table below:

Outcome	Type of Outcome	Assessment Tool	Assessment timepoints	Sample size
Treatment engagement	Primary	Medical records and study database	Prenatal treatment period	264

Treatment retention	Primary	Medical records and study database	Birth and 3-months post-partum	264
Patient Activation	Primary	Patient Activation Measure	Baseline, 26 weeks ,36 weeks and 3 months post-partum	264
#/% initiated onto MAT	Secondary	Medical records and study database	Prenatal treatment period	264
#/% retained on MAT	Secondary	Medical records and study database	Birth	TBD
Birth weight	Secondary	Medical records and study database	Birth	264
Physician Work Satisfaction	Secondary	Physician Work Life Survey	Before first participant enrollment and after last participant enrollment	12
#/% increasing at least one PAM level	Secondary	Patient Activation Measure	Week 36 and 3-months post-partum	264
#/% offered MAT	Exploratory	Medical records and study database	Prenatal treatment period	264
#/% continuing MAT at 3 months postpartum	Exploratory	Medical records and study database	3-months post-partum	TBD
#/% engaging in an opioid treatment program at 3 months post delivery	Exploratory	Medical Records and study database	3-months post-partum	264
#/% abstinent from illicit opioids or misuse or prescription opioids	Exploratory	a. TLFB b. Urine Drug screens	a. monthly b. each prenatal visit and birth and post birth	264
#/% with concurrent substance use	Exploratory	a. TLFB b. Urine Drug screens	a. monthly b. each prenatal visit and birth and post birth	264
Low birth weight	Exploratory	Medical records and study database	birth	264
Resuscitation at delivery	Exploratory	Medical records and study database	birth	264
Fetal demise	Exploratory	Medical records and study database	birth	264
Preterm birth	Exploratory	Medical records and study database	birth	264

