and 36 weeks (+/- 4 weeks), and at 3M post-partum. Data will be collected using a tablet provided by the DSP. In addition, maternal/infant medical record data will be extracted by the DSP and provided to the Yale and UMass data collection teams. These data will include maternal, fetal and neonatal outcomes.

In addition to the above recruitment strategies, we will also ask women who participate in the study if they know any other women who might be interested in participating. We will explain to the participant that if they know any other pregnant women who may have an opioid use disorder (i.e. known or suspected use of illicit opioids or known to be on MAT) that they can let the women know about the Project Smart Study and give our contact information. We will give our business cards to any women who think they might know someone who would be interested and they will need to contact us directly. Due to the sensitive nature of the study, we will not collect any contact information about the potential participant; she will need to contact us from the information on the business card and thus show her interest in the study.

Participants who recommend someone who consents and is eligible for the study will be compensated with a \$25 Amazon gift card for the referral.

A subset of patient participants in the trial will be given the opportunity to participate in a separate qualitative interview. These interviews will collect data on patient level of satisfaction with MAT experiences at the clinics.

The experiences of physicians involved in the project will also be assessed. At least one provider from each practice (minimum of 12) will also be invited to participate in qualitative interviews to assess their perceptions of the implementation of MAT within their practice including barriers and facilitators to implementation. All providers who participated will be asked to complete brief forms asking about workload and clinical support.

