### 5.3 LIFESTYLE CONSIDERATIONS

During this study, participants are asked to:

- Come to visits as scheduled
- Continue or begin any behavioral or medication assisted OUD treatment (MAT).
  - Note the MAT status of patients can vary: women may choose to receive buprenorphine, they may receive methadone from another provider, or they may choose to receive no MAT. We would also allow women to change their decisions about MAT; we would like to respect their choice and they may decide later to engage in MAT. We will also include women who are on methadone since they may prefer to switch to buprenorphine or no MAT.

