## Secondary Hypotheses:

$H_1$ : Participants with an OUD are more likely to be engaged in MAT if the center is randomized to the CC vs the ECHO model of support.

$H_2$ : Participants with an OUD treated in CC centers are more likely to be retained in MAT for an OUD than those treated in a center randomized to the ECHO model of care.

$H_3$ : Babies born to mothers treated in CC centers will have higher birth weights on average compared to babies born to mothers treated in ECHO centers.

$H_4$ : Obstetrical providers randomized to the CC compared to the ECHO condition will score higher on subscales (autonomy, relationship with patients, patient care issues and relationship with staff) of the Physicians Worklife Survey.

$H_5$ : Participants in the CC, compared to the ECHO condition, are more likely to increase at least one PAM level from baseline to week 36 and 3-months post-partum.

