**9.4.8 EXPLORATORY ANALYSES**

Exploratory analyses will compare care models for eligible women (gravidas with an OUD, not in treatment when presenting for prenatal care) on the following outcomes: 1) #/% offered MAT including buprenorphine, specifically; and 2) rates of abstinence from illicit opioids or misuse of prescription opioids. (107) Additionally, for all pregnant women treated with MAT: 3) #/% continuing MAT at 3 months postpartum; 4) #/% engaging in an opioid treatment program at 3 months post-delivery. We will also explore differences between care models in: 5) #/% with concurrent substance use according to the **Time Line Follow-Back (TLFB)** (107) and urine tests; 6) fetal and neonatal outcomes (low birth weight, resuscitation at delivery, fetal demise, preterm birth, duration of hospitalization).

Exploratory analyses will also compare models in terms of participant reported differences in: 1) the **Shared-Decision Making Questionnaire-9 (SDM-Q-9)** (108); 2) **Perceived efficacy in Patient-Physician Interactions Questionnaire (PEPPI)** (109); 3) Kim Alliance Scale-Communication subscale (**KAS-CM**) (110); 4) PROMIS Emotional Short Form(111) and Satisfaction with Roles and Activities(111); and 5) **Edinburgh Postnatal Depression Scale (EPDS)**(112, 113) .

We will explore racial and ethnic differences on patient measures and possible differences in outcomes among those who were users of illicit street opioids vs misusers of prescription opioids.

**10 SUPPORTING DOCUMENTATION AND OPERATIONAL CONSIDERATIONS****10.1 REGULATORY, ETHICAL, AND STUDY OVERSIGHT CONSIDERATIONS****10.1.1 INFORMED CONSENT PROCESS**

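### The MAT initiation outcome is tabulated on the full enrolment of 264 with no at-risk restriction or adjustment for MAT use at entry, and it does not match the MAT engagement hypothesis

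*Combined protocol and SAP*

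**What the plan says.** **Outcome table, section 3.** The row "initiated onto MAT" is secondary, is assessed over the prenatal treatment period and has sample size 264. Initiation is not defined. The next row, "retained on MAT", has its sample size still to be determined.

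**Hypothesis, section 9.1.** Secondary H1 reads "Participants with an OUD are more likely to be engaged in MAT if the center is randomized to the CC vs the ECHO model". The first secondary aim in section 3 says the same. Section 9.2 also names engagement with MAT among the secondary outcomes, as one for which power could not be assessed.

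**Definition of engagement, section 6.4.** For the primary outcome, engagement means a minimum of one visit a month over three months, counting MAT and/or non-drug treatment. There is no MAT-only version.

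**Who may enrol.** Sections 5.1 and 5.2 do not exclude current MAT. Section 5.3 states "We will also include women who are on methadone since they may prefer to switch to buprenorphine or no MAT", and section 6.5 repeats it. Section 4.1 describes women who may be referred by other participants as having "known or suspected use of illicit opioids or known to be on MAT".

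**Analysis.** Section 9.4.3 sends secondary patient outcomes to the model of section 9.4.2, which has a random site effect and a fixed intervention effect. A baseline covariate is named only for PAM. MAT status at entry is not among the individual-level covariates in section 9.4.6.

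**A restriction used elsewhere.** Section 9.4.8 limits the exploratory outcomes on being offered MAT and on abstinence to "eligible women (gravidas with an OUD, not in treatment when presenting for prenatal care". The table still prints 264 for both.

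**The concern.** A woman on MAT when she enrols brings that status with her; the support model did not produce it. The plan does not say whether she counts as initiated, as not initiated, or as outside the denominator. If she is counted either way among all 264, part of the result reflects who was enrolled.

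This could differ between arms. Sites are randomised first (section 6.2.1), and their own staff then enrol the women; in the collaborative care sites this is the care manager (section 5.5). With 12 sites, chance imbalance in entry status is also plausible.

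The label is a second problem. A woman could start MAT without meeting any sustained-visit rule. Reporting initiation under a hypothesis about engagement would answer a different question, and the choice between the two would stay open until the data are seen.

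**Working it through.** **1. What 264 is.** Sections 5.5 and 9.2 give 12 sites, 20 women per site and 10% attrition. 12 × 20 = 240, and 240 × 1.10 = 264. (Dividing by 0.90 would give 267.) So 264 is total enrolment, 132 per arm, with nothing removed for women on MAT at entry. The plan gives no power figure for this outcome to reproduce.

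**2. Dilution.** Let f be the share on MAT at entry, equal in both arms, and let p be the proportion initiated among the other women. On the full denominator:
- entry users counted as not initiated: (1 − f)p
- entry users counted as initiated: f + (1 − f)p

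Under either coding the difference between arms is (1 − f)(p_CC − p_ECHO). The documents do not give f. The values below are assumptions. The 37% and 46% are the MAT rates that section 2.2 cites among pregnant treatment admissions, a different population, so they serve only as illustrations.

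| f (assumed) | A 20-point difference becomes | Women not on MAT, 264 × (1 − f) | Per site |
|---|---|---|---|
| 10% | 18.0 points | 238 | 19.8 |
| 20% | 16.0 | 211 | 17.6 |
| 30% | 14.0 | 185 | 15.4 |
| 37% | 12.6 | 166 | 13.9 |
| 46% | 10.8 | 143 | 11.9 |
| 60% | 8.0 | 106 | 8.8 |

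**3. Imbalance with no true effect.** Let p be the same in both arms and let the entry shares be f_CC and f_ECHO. The apparent CC minus ECHO difference is:
- counted as not initiated: p(f_ECHO − f_CC)
- counted as initiated: (1 − p)(f_CC − f_ECHO)

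With assumed p = 0.60, f_CC = 37% and f_ECHO = 46%:
- counted as not initiated: 0.60 × 0.63 = 0.378 against 0.60 × 0.54 = 0.324, or +5.4 points
- counted as initiated: 0.37 + 0.378 = 0.748 against 0.46 + 0.324 = 0.784, or −3.6 points

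The coding choice alone reverses the direction.

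**4. The engagement rule near term.** Section 5.1 admits women up to 34 weeks of gestation. The synopsis gives about 44 weeks of participation, from 8 weeks of pregnancy to 3 months after birth. Taking 3 months as about 12 weeks, that implies delivery near 8 + 44 − 12 = 40 weeks. A woman enrolled just before 34 weeks has little more than 6 prenatal weeks, so a three-month rule cannot be completed before birth.

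**The case against.** Several stronger readings are tempting, and the documents do not support them.

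- **That the analysis will certainly use all 264.** A reader might infer this from the table, but sections 9.3 and 9.4.3 state no denominator for this row. The table prints 264 for three outcomes that section 9.4.8 restricts: being offered MAT, abstinence, and engaging in an opioid treatment program. The entries still to be determined show that the column sometimes separates denominators, but it does not do so reliably. What stands is that no at-risk denominator is stated anywhere.
- **That a woman on MAT cannot be initiated.** Section 6.1.1 uses initiation for starting buprenorphine, and section 5.3 includes women on methadone partly because they may switch to it. Whether a switch counts is undefined. Nor do the documents define initiation as a first dose.
- **That initiation and engagement are plainly two planned endpoints.** Section 6.4 contrasts its broader outcome with simply starting and continuing MAT, which suggests that the authors may see initiation as the MAT-only counterpart of engagement. That would explain one outcome under two labels. It does not supply a definition.
- **That the bias is known or large.** The entry shares and initiation rates above are assumed. The 5.4-point gap is slightly below one standard error even before clustering: √[(0.378 × 0.622 + 0.324 × 0.676)/132] = 0.059.

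It can also be said that MAT receipt among all enrolled women is a legitimate intention-to-treat quantity. That is true, but it is receipt, and the row would then need that name and an adjustment for entry status.

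**Conclusion.** The point holds for one secondary outcome. The row carries the full enrolment, women on MAT may enrol, the model has no term for MAT status at entry, and the hypothesis names a different outcome. Taken as tabulated, a true difference among women not on MAT shrinks by the factor 1 − f. That is 20 points to between 18 and 8 for an assumed f of 10% to 60%, with f equal in the arms. Unequal entry shares can create a difference in either direction without any effect. The actual size cannot be fixed from the documents, because f is not given. The primary outcomes are not affected by this row.

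**What to change.** (a) **Initiation.** Analyse it among women not receiving MAT at baseline, identified from the Treatment Utilization Form, which section 1.3 schedules at screening and Visit 1. Restate the sample size as below 264. State whether a switch from methadone to buprenorphine counts.

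(b) **Secondary H1.** Add a row for engagement in MAT in all enrolled women, with baseline MAT status (yes/no) as a fixed effect in the mixed model. State how the monthly-visit rule of section 6.4 applies to women who enrol too late to have three prenatal months. Use the same outcome name in sections 3, 9.1 and 9.2.

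(c) **The row for being offered MAT.** Make its sample size agree with the restriction in section 9.4.8.

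**Cost.** These are wording changes to the plan and table, using data already scheduled for collection. The initiation analysis will have fewer women: 238 down to 106 over the assumed range.

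**Limit.** The change reduces the influence of imbalance in entry MAT status. It does not remove other differential recruitment after site randomisation, because the same site staff also recruit the women not on MAT.

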## 4 STUDY DESIGN

### 4.1 OVERALL DESIGN

Yale will lead this study to compare the effectiveness of two models of support for reproductive health clinicians who will provide prenatal and addiction care for pregnant and postpartum women with an opioid use disorder in obstetrical centers in Connecticut and Massachusetts. The two models being compared are: 1) a collaborative care (CC) approach, based upon the Massachusetts Office-Based-Opioid Treatment Model, that would provide onsite training, and support to providers through the use of a care managers; and 2) a tele-support approach modeled on the Project Extension for Community Healthcare Outcomes (ECHO), a remote education model that provides mentorship and guided practice and participation in a learning community via video conferencing. Twelve obstetrical centers who currently do not have a system in place to treat pregnant women with OUD will be recruited and their characteristics matched. The unit of randomization is the obstetrical center. We will randomly assign one center in each pair to either the CC or ECHO model, 6 sites to each model of support. A statistician, blinded to the identities of the clinics, will assign a number to each clinic using a random number generator; within each matched pair, the clinic with the lower number will be assigned to CC and the other will be assigned to ECHO. Among the centers, we would recruit 264 women in total, 132 women from the CC sites and 132 from the ECHO sites, about 20 per site among the 12 sites.

Although we will recruit centers that report caring for at least 40 women per year who have an OUD, we will need an accurate method for estimating the rate of opioid use in order to compute outcomes. we will obtain the base rate of opioid and other illicit substance use in each practice by obtaining urine drug screens from all women attending the obstetrical practice for a prenatal visit in a one-week period. Urine collection will be anonymous and will use a small portion of the sample women typically provide at each prenatal visit. Clinic staff will collect urine samples from their patients as normal. A Yale research assistant will then test a small portion of the sample with an instant urine toxicology test.

Results will be entered anonymously into a REDCAP@yale database and assigned a random subject number. Research assistants will have no contact with the patients themselves and no identifying information will be collected. Results of the urine collections will be used to determine the prevalence of substance use at each study practice. This procedure will be repeated annually during the study to ensure the accuracy of the estimate.

Recruitment of patient participants will be facilitated by universal screening by practice sites and referral to the study if appropriate. Screening for opioid misuse will occur at prenatal visits as recommended by the American College of Obstetricians and Gynecologists. Clinicians will follow up on affirmative answers and discuss study participation with them. A designated staff person (DSP) will hand potentially eligible women a tablet that includes screening questions and a patient consent document. After reviewing the consent form, and having any questions answered and signing the consent form, study participants will then complete a baseline assessment that includes demographic information and questions about pregnancy dates and a checklist that would indicate an opioid use disorder (OUD) (via a tablet computer). After completion of these questions, the tablet and DSP will determine whether the woman remains eligible for participation and will be enrolled. The participant will be assigned a study identification number. She will then complete additional questions that are part of the baseline assessment for Visit 1 (see Table 1).

Potentially eligible women will also be given the option of having a researcher contact them by phone and reviewing the consent via phone or Yale Zoom if that is their preference. In this scenario, women will provide verbal consent to the DSP at the practice site if they are interested in being contacted by study staff, and the obstetrical provider will provide her name and contact information to research staff. Referred women will be contacted by phone or by a research assistant who will explain the entire protocol and all of its requirements at length. Additionally, women are encouraged to ask questions about any confusing points. Subjects are told that they may withdraw from the project at any time, without prejudice, and without any adverse effect on their medical care at their prenatal clinic. Women who express interest in study participation will be emailed or texted a link of the study consent form using REDCap@yale. Participants will be provided with time to review the content and the researcher will then review the eConsent form, and answer any remaining questions. Once the participant has signed and submitted the eConsent form the research assistant will receive a REDCap notification of its submission and will review the form to confirm it is filled out correctly. The research assistant will then open the corresponding 'Person Obtaining Consent' form as a survey and electronically sign it. Screening and baseline assessments as described above will then be emailed or texted to the participant.

After enrollment, a urine drug screen (UDS) will be obtained at each prenatal visit (the urine will be collected as part of the regular prenatal visit and tested for the presence of illicit and licit opiate drugs). Study sites will be asked to report results of UDS by completing a form that is entered into REDCap. Participants will also be contacted monthly by a Yale research assistant (who is blind to condition) to complete a **Time Line Follow-Back (TLFB)** and the **Treatment Utilization Form** that includes questions about the quantity and frequency of all substances used and treatment received. Study participants will complete additional self-report questionnaires at the following assessment points: enrollment, 26 weeks

and 36 weeks (+/- 4 weeks), and at 3M post-partum. Data will be collected using a tablet provided by the DSP. In addition, maternal/infant medical record data will be extracted by the DSP and provided to the Yale and UMass data collection teams. These data will include maternal, fetal and neonatal outcomes.

In addition to the above recruitment strategies, we will also ask women who participate in the study if they know any other women who might be interested in participating. We will explain to the participant that if they know any other pregnant women who may have an opioid use disorder (i.e. known or suspected use of illicit opioids or known to be on MAT) that they can let the women know about the Project Smart Study and give our contact information. We will give our business cards to any women who think they might know someone who would be interested and they will need to contact us directly. Due to the sensitive nature of the study, we will not collect any contact information about the potential participant; she will need to contact us from the information on the business card and thus show her interest in the study.

Participants who recommend someone who consents and is eligible for the study will be compensated with a \$25 Amazon gift card for the referral.

A subset of patient participants in the trial will be given the opportunity to participate in a separate qualitative interview. These interviews will collect data on patient level of satisfaction with MAT experiences at the clinics.

The experiences of physicians involved in the project will also be assessed. At least one provider from each practice (minimum of 12) will also be invited to participate in qualitative interviews to assess their perceptions of the implementation of MAT within their practice including barriers and facilitators to implementation. All providers who participated will be asked to complete brief forms asking about workload and clinical support.

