### 5.5 STRATEGIES FOR RECRUITMENT AND RETENTION

Participants will be enrolled at 12 obstetrical centers that are matched on demographics of patient population. Within each pair of centers, each will be randomly assigned to the CC or ECHO condition. We will enroll 264 women in total, half in each treatment condition.

Recruitment was impacted by the Covid-19 Pandemic, and we re-evaluated our recruitment plan based upon our first 16 months of recruitment (10.25.21). We reduced our anticipated sample size to 264 participants in total or 132 in each treatment group with an average of 20 participants per site, allowing for 10% attrition. For the engagement outcome, we anticipated screening 360 eligible patients.

Women will be enrolled at each site by a designated staff person (DSP), most likely a nurse (at the CC practices it will be the CM). We will be placing recruitment flyers and posters in the two clinic sites advertising the study. We will have a social media page that describes the project. A QR Code on the flyers and poster will direct potential participants to the social media page. There the woman can read about the study or choose to watch a short video describing the study. As recommended by ACOG,(33) the DSP will administer their standard opioid screening to all pregnant women at all sites. Women with a positive screen will be invited to participate. DSPs will then obtain written consent from patients who agree to participate in the trial or remote consenting will be done as described earlier. The DSM-5 checklist will be completed for the diagnosis of OUD. Women who meet criteria for OUD will be deemed eligible to participate in the trial. To minimize attrition, the DSP will then: 1) explain the importance of follow-ups, 2) rapidly schedule first visit with a provider associated with the study after confirmation of eligibility and consent, 3) collect at least 3 verified locators, 4) call women to remind them of their appointments, and will have contact with a significant other who can provide collateral information and maintain subject involvement. Investigators will monitor participants who drop out and explore with the staff reasons for the dropouts.

In addition to patient participants in the trial, qualitative interviews will be conducted with a subset of patient participants and physicians involved in the project. Patient participants will be contacted, consented and enrolled in this portion of the project by computer randomization.

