### 6.3 MEASURES TO MINIMIZE BIAS: RANDOMIZATION AND BLINDING

Matching of Clinics- Participating clinics will be matched as closely as possible based on state, size and academic vs. non-academic / community hospital to lessen site interactions with the data.

Randomization of Clinics- Within each matched pair, one clinic will be randomly assigned to the CC condition and one will be assigned to the ECHO condition. Randomization will occur by assigning a number to each clinic using a random number generator; within each matched pair, the clinic with the lower number will be assigned to CC and the other will be assigned to ECHO.

Blinding of Research Staff- The statistician will be blinded to the identities of the clinics when assigning treatment allocation during randomization. Research staff who will contact the participants to conduct the monthly TLFB will be blinded to the treatment condition. In addition, the research staff who extract the maternal and infant outcome data

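### In the collaborative care arm, the care manager who delivers the intervention may also extract the records behind engagement and retention, and no masked classifier or deciding source is named

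*Combined protocol and SAP*

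**What the plan says.** The outcome table in section 3 gives the assessment tool for treatment engagement and treatment retention as "Medical records and study database". Section 4.1 states that "maternal/infant medical record data will be extracted by the DSP and provided to the Yale and UMass data collection teams", and continues: "These data will include maternal, fetal and neonatal outcomes". Section 5.5 has women enrolled by a "designated staff person (DSP), most likely a nurse (at the CC practices it will be the CM").

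Section 6.1.1 makes the care manager (CM) responsible in CC for the patient registry, patient education, help with treatment initiation, and recovery coaching. Section 6.4 counts CM visits as behavioral therapy in CC when they focus specifically on addiction treatment. It defines failed retention as stopping treatment for two months with no plan for ongoing therapy or medication. It does not say who makes either judgment.

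Section 6.3, in its paragraph on blinding of research staff, ends with "In addition, the research staff who extract the maternal and infant outcome data". The sentence has no predicate in the text supplied.

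There is also a blinded source. Section 4.1 says: "Participants will also be contacted monthly by a Yale research assistant (who is blind to condition) to complete a" Time Line Follow-Back and the Treatment Utilization Form, which cover treatment received. Section 6.1.1 says that data collection in ECHO will mirror CC and be done by a person whom the practice designates.

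**The concern.** Two things could tilt the comparison toward CC.

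The first is classification. In CC, the person who delivers recovery coaching documents visits that can count toward the outcome, and she may also extract the record that shows them. Whether a visit was addiction-focused, or whether a woman who stopped had a plan for ongoing care, needs judgment. She is not blinded. The ECHO DSP is not blinded either, but ECHO has no designated role whose own visits are credited in this way.

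The second is capture. Women may receive methadone or behavioral therapy elsewhere (5.3, 6.5). CC has a registry and a CM who supports women on methadone and collects their urine results (6.1.1). In ECHO a nurse may take on CM tasks, but this is not required (6.2.1). Off-site care could therefore reach the CC record more often.

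Both effects would favor the hypothesis, and a larger sample would not remove them. The sensitivity analyses in 9.3 deal with missing data. A visit that was never charted is not flagged as missing; it reads as not engaged or not retained.

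**Working it through.** **Step 1: follow the outcome to its source.** Section 3 names records and the study database. Section 4.1 has the DSP extract record data. Section 5.5 makes the CM the DSP at CC practices. Section 6.4 credits CM visits. The chain from interventionist to part of a primary outcome is therefore open in CC. No section says which source decides when the record and the monthly form differ, or who classifies. The annual urine-based estimate in 6.4 concerns the denominator and does not close this gap.

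**Step 2: compare the two descriptions of the extractor.** Section 4.1 names the site DSP. Section 6.3 refers to research staff, under a blinding heading. These must be reconciled, whatever the missing end of the 6.3 sentence says.

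**Step 3: the yardstick.** Section 9.2 plans for 0.94 against 0.74, a difference of 0.20 with 80% power, at 6 clusters per arm, 20 women per cluster and coefficient of variation k = 0.10. With v = p0(1−p0)/m + p1(1−p1)/m + k²(p0²+p1²):

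- At m = 20, v = 0.00962 + 0.00282 + 0.01431 = 0.02675.
- Unmatched form: power = Φ(0.20·√(5/v) − 1.96) = Φ(0.774) = 78.1%, and 79.8% at m = 22, close to the stated figure.
- Matched-pair form, with 4 in place of 5: 68.6% at m = 20.

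That mismatch is a separate matter. Only the 0.20 is used below.

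**Step 4: false difference if records were the only source.** The documents give no capture rates, so these are assumptions. With the same true retention p in both arms, complete capture in CC and capture s in ECHO, the false difference is p × (1 − s).

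| ECHO capture s | p = 0.74 | p = 0.94 |
|---|---|---|
| 95% | 0.037 | 0.047 |
| 90% | 0.074 | 0.094 |
| 85% | 0.111 | 0.141 |
| 80% | 0.148 | 0.188 |

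At p = 0.94, ECHO capture of 0.74/0.94 = 79% would by itself produce the planned 0.20.

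**Step 5: allow for the monthly form.** If the form recovers a share r of what the record misses, the false difference becomes p × (1 − s) × (1 − r). With r = 50% (assumed), the range 0.037 to 0.188 falls to 0.019 to 0.094. With r = 80% (assumed), it falls to 0.007 to 0.038.

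**Step 6: effect on the test.** Take CC recorded at 0.94, m = 20, k = 0.10 and 6 clusters per arm. A false difference of 0.05 gives v = 0.004895 + 0.00282 + 0.016757 = 0.02447 and z = 0.05/√(v/6) = 0.78. It would be declared significant in about 12% of trials (normal), or 11% (t, 10 degrees of freedom), against a nominal 5%. For 0.10 the figures are 34% and 29%. This approximates the planned mixed model.

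**The case against.** The strongest reply is that the documents do not show DSP extraction to be the only, or even the main, source of engagement and retention. The sentence on what the extract contains names maternal, fetal and neonatal outcomes, not treatment engagement or retention. The CM's research tasks in 6.1.1 are consent, urine results and the self-report battery. The study database is a second source, off-site therapy is recorded in the eCRF (6.5, 8.1.1), and blinded staff ask about treatment every month in both arms (4.1, 8.1.3). ECHO collection is said to mirror CC. All of this stands, and it limits the size of any bias. It does not say which source decides.

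A reader might go further and infer that section 6.3 promises blinded extraction and 4.1 breaks that promise. The text does not support this. The 6.3 sentence is incomplete, possibly through conversion from PDF, and never states that the extractors are blinded.

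A reader might also want the blinded monthly form to decide the outcome alone. That is doubtful for three reasons. Section 6.4 requires visits with billable treatment providers and, for the CM, a specific addiction focus, neither of which a phone report can reliably establish. The schedule in 1.3, as supplied, does not mark the form at birth or at 3 months post-partum. And a woman who describes recovery coaching may reveal her condition to the caller.

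**Conclusion.** The concern holds in a limited form. As written, the plan lets the CC interventionist extract records that may feed two primary outcomes and names no independent classifier, although some of the visits counted are her own. It also gives two descriptions of the extractor.

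A reader might infer that these outcomes are in fact ascertained more completely in CC. The documents make this plausible but do not show it: they give no capture rates and state that ECHO collection mirrors CC. The false difference of about 0.04 to 0.19 rests on equal true retention of 0.74 to 0.94, complete CC capture, ECHO capture of 95% to 80%, and records as the only source. It shrinks to the extent that the monthly form recovers missed care. These figures show that such a bias would matter if present, not that it is present. The weakness should be repaired, because the repair is cheap and the direction of any bias favors the hypothesis.

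**What to change.** Amend 4.1, 6.3 and 6.4 so that they agree:

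- The DSP or CM supplies source records only.
- Existing central research staff, masked to condition, classify engagement and retention in both arms by one written rule that combines the records with the blinded monthly Treatment Utilization Form. The rule says what happens when the two differ.
- The same staff, not the CM, decide whether a CM visit qualifies.
- Self-report is not the sole deciding source.

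In section 9.4, add a report of agreement between record and form by arm, and a sensitivity analysis based on the blinded form for the period in which it is collected. Confirm whether the monthly calls continue after birth, since 1.3 does not mark the form at birth or 3 months post-partum. If they stop, say that post-partum retention rests mainly on records.

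The cost is protocol and SAP wording plus some central coding and redaction. Masking may be imperfect where a record mentions the care manager, and this should be acknowledged.
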